## 8.0 STATISTICAL ANALYSES

### 8.1 Subject Disposition

The number of percentage of subjects in screened, randomized, FAS population, Safety Population, PP Population, completed the study and discontinued from the study will be reported, along with the reason for discontinuation.

Percentages will be out of the number of safety population. Counts only will be reported for screened subjects.

### 8.2 Demographic and Baseline Characteristics

Demographic/baseline characteristics will be summarized descriptively by treatment group in Safety Population.

The following variables will be included:

- Age (years)
- Sex (male, female)
- Race (White, Black or African American, Asian, American Indian or Alaska Native, Native Hawaiian or Other Pacific Islander, Other)
- Ethnicity (Hispanic or Latino, Not Hispanic or Latino)
- Height, Weight and Body Mass Index (BMI) (*Screening*)
- Height (cm)
- Weight (kg)
- BMI (kg/m^2)
- SARS-CoV-2 quantitative RT-PCR result (*Screening*)

### 8.3 Medical History

Medical history terms will be coded using the Medical Dictionary for Regulatory Activities (MedDRA) dictionary. Medical history will be summarized by system organ class (SOC) term and preferred term for each cohort by treatment group. For subjects with the same SOC and preferred term occurring more than once, the first occurrence will be tabulated.

Conditions will be listed, including the verbatim investigator description of the relevant medical condition, the coded terms (SOC, preferred term), start date, end date, and whether or not the condition is ongoing.

### 8.4 Prior and Concomitant Medications

Prior medications are defined as all medications recorded in the CRF initiated prior to the start of the study treatment. Prior medications will be coded with the World Health Organization Drug

---

Dictionary (WHO-DD), and summarized by drug class (Anatomical Therapeutic Chemical [ATC] Level 3) and preferred term; a subject will be counted only once for each medication.

All medication will be listed with the prior medications flagged.

## **8.5 Protocol Deviations**

Protocol deviations recorded will be reviewed and major deviations will be identified prior to database lock and unblinding of the study. The PP population will be determined and subjects with major protocol violations, entry criteria violations or missing visits will be excluded.

## **8.6 Study Drug Administration**

Two STI-5656 or matching placebo capsules p.o. QD (two 50-mg capsules) are administered orally up to 14 days or until hospital discharge if sooner. If vomiting occurs within 30 minutes after a patient takes the dose and the patients can tolerate the medication, the vomited dose should be made up.

If the subject is unable to swallow, the capsule contents may be flushed down a nasogastric or feeding tube with water.

For study drug administration, descriptive statistics of the following parameters will be presented.

- Number of days on study treatment
- Total dose planned
- Total dose administered
- Total dose missed
- Compliance rate, defined as the total dose administered/total dose planned, expressed as a percentage.

Subject listing of study drug administration will be presented.

## **9.0 EFFICACY EVALUATION**

### **9.1 Primary Endpoint**

The primary efficacy endpoint is the proportion of subjects alive and free of respiratory failure at Day 28, where respiratory failure, is defined based on resource utilization of any of the following modalities:

- Noninvasive positive pressure ventilation or continuous positive airway pressure
- Endotracheal intubation and mechanical ventilation
- Oxygen delivered by high-flow nasal cannula (heated, humidified, oxygen delivered via reinforced nasal cannula at flow rates  $>20$  L/min with fraction of delivered oxygen  $\geq 0.5$ )
- Extracorporeal membrane oxygenation

The number and percentage of subjects will be presented by treatment group using FAS population. Primary analysis to evaluate the differences between groups will utilize a

generalized linear mixed model, assuming a binomial distribution and a logit link. The model will include group as a fixed effect. Subjects who discontinue the study prior to Day 28 will be considered treatment failures.

Sensitivity analyses may be performed using PP population.

After 40 subjects have been enrolled and completed Day 28, an interim futility analysis will be performed to examine the proportion of subjects alive and free of respiratory failure at Day 28. The interim analysis is a non-binding analysis. See Section 7.4 for details.

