## **1.0 INTRODUCTION OF THE STATISTICAL ANALYSIS PLAN**

The statistical analysis plan (SAP) is based on protocol STI-5656-2001 ‘A Phase 2, Randomized, Double-Blind, Placebo-Controlled Study of The Safety and Efficacy of Sti-5656 (Abivertinib Maleate) In Subjects Hospitalized Due to Covid-19’, V5.0 dated 07Dec2020. It details the methodology to be used in analyzing the data and outlines the specifications in the Tables, Figures and Listings (TFLs) for data to be included for executing the final statistical analyses for this study.

PK analysis is not included in this plan.

The analyses specified in this document supersede any high-level analysis plan described in the protocol.

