## **5.0 SAMPLE SIZE CONSIDERATIONS**

An evaluable sample size of 40 subjects per group will provide 80% power (alpha=0.05, 2-sided) to detect a difference between groups in the number of subjects alive and free of respiratory failure at Day 28. This assumes that 95.7% of subjects who received STI-5656 plus SOC and 70% of subjects who received placebo plus SOC only will be alive and free of respiratory failure at Day 28. This represents a treatment effect difference of approximately 26%.

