### 7.4 Interim Analysis

A non-binding interim futility analysis will be performed after 40 subjects have reached the study primary endpoint. The analysis will be performed by an independent biostatistician who will have no contact with the study team.

This interim analysis will use non-binding futility boundaries. At 50% planned subjects (40 subjects out of 80 subjects total), futility interim will be performed. O'Brien-Fleming beta spending function will be used. Futility bound on Z scale is 0.537. The futility bound is crossed if an observed Z statistic is less than 0.537. Nominal beta is 0.296 with cumulative beta being 0.065 at the interim and 0.192 at the final analysis. The above interim planning was performed under 1-sided test setting using nQuery Version 8.6.1.0. Using 1-sided alpha of 0.025, with

continuity correction, sample size of 40 per group (80 total) have 80.8% power (beta 0.192) to detect the difference of 95.7% in active arm vs 70% in control arm.

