## 9.2 Secondary Endpoints

### 9.2.1 Proportions

The same method used in the primary endpoint will be repeated for the following secondary efficacy endpoints:

- Proportion of subjects alive and free of respiratory failure at Day 60
- Proportion of subjects alive and discharged from ICU at Days 14 and 28
- All-cause mortality at Day 60 and Day 90

Subjects who discontinue the study prior to the study day end will be considered treatment failures.

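### SAP 9.1 names neither the test of the group effect nor a rule for an arm with no failures, an outcome up to 17.2% likely in the active arm at the design rate

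*SAP*

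**What the plan says.** SAP 9.1 compares the proportions alive and free of respiratory failure at Day 28 with a "generalized linear mixed model, assuming a binomial distribution and a logit link". On the terms it says only: "The model will include group as a fixed effect". It names no random effect, estimation method, test of the group coefficient or fallback for a fit that does not converge. On dropouts it says: "Subjects who discontinue the study prior to Day 28 will be considered treatment failures". The analysis set is the FAS, all randomized subjects (SAP 6.1).

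Protocol 9.4.3 describes the same model and is equally silent on the test. The SAP governs in any case: "The analyses specified in this document supersede any high-level analysis plan described in the protocol".

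The design success rates are in SAP 5.0: "This assumes that 95.7% of subjects who received STI-5656 plus SOC and 70% of subjects who received placebo plus SOC only". That section claims 80% power at two-sided 0.05 for 40 evaluable subjects per group. SAP 7.4 gives 80.8% (beta 0.192) for the same rates at one-sided 0.025 with a continuity correction. SAP 7.4 also refers to an observed Z statistic, but for the interim futility bound only, and does not define it.

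SAP 9.2.1 carries the method forward: "The same method used in the primary endpoint will be repeated for the following secondary efficacy endpoints". The endpoints listed are Day 60 freedom from respiratory failure, ICU discharge at Days 14 and 28, and mortality at Days 60 and 90.

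**The concern.** In a logit model with group as the only factor, an arm without failures has an infinite maximum-likelihood log odds. Wald, likelihood-ratio and exact tests then give very different answers, so the unnamed test can decide the trial. The empty cell is not remote: the design assumes an active rate close to 1 with only 40 subjects in the arm.

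Two analysts could both follow SAP 9.1 to the letter and reach opposite conclusions from the same table. If the test is settled after the empty cell has been seen, the choice is a data-driven change to the primary analysis. It would arise exactly when the active arm has done as well as it can. The power statement is affected too, since it was computed for a continuity-corrected comparison of two proportions and not for the model in SAP 9.1.

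**Working it through.** **Inputs.** From SAP 5.0 and 7.4: 40 per arm, active 0.957, control 0.70, two-sided 0.05. From SAP 9.1: group as sole term, discontinuation counted as failure. Assumptions: no random effect, normal reference for Wald, futility look ignored. The documents give no discontinuation rate. The 2%, 5% and 10% below are assumptions and multiply both success rates by 0.98, 0.95 and 0.90.

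**The plan's own figure.** Pooled rate (0.957 + 0.70)/2 = 0.8285. Null SE = sqrt(2 × 0.8285 × 0.1715/40) = 0.0843. Alternative SE = sqrt((0.957 × 0.043 + 0.70 × 0.30)/40) = 0.0792. With the continuity correction 1/40, power = Φ[(0.257 − 0.025 − 1.96 × 0.0843)/0.0792] = Φ(0.84) = 80.0%. The stated 80% reproduces, and 80.8% is within a point of it. The planning figure is therefore sound for a corrected two-proportion comparison.

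**Probability of 40/40 in the active arm.**
- No discontinuation: 0.957^40 = 17.2%
- 2%: (0.957 × 0.98)^40 = 7.7%
- 5%: (0.957 × 0.95)^40 = 2.2%
- 10%: (0.957 × 0.90)^40 = 0.3%

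**The Wald statistic.** With a and b successes of 40, Z = [log(a/(40 − a)) − log(b/(40 − b))] / sqrt(1/a + 1/(40 − a) + 1/b + 1/(40 − b)).
- 39/40 vs 32/40: (log 39 − log 4)/sqrt(1/39 + 1 + 1/32 + 1/8) = 2.277/1.087 = 2.09, p = 0.036.
- 40/40 vs any b: replace the zero failures by a small e. The numerator grows like log(1/e) and the denominator like 1/sqrt(e), so Z tends to 0 as the fit converges.
- 40/40 vs 28/40 has Fisher p = 2 × C(40,12)/C(80,12) = 0.0002.

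Fisher's test rejects 40/40 against a control result of 34/40 or fewer (p = 0.026 at 34, 0.055 at 35). At a control rate of 0.70 that covers 99.1% of trials with a 40/40 active arm, so a converged Wald test gives up 17.2% × 0.991 = 17.1 points.

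**Exact power (%), all 41 × 41 tables enumerated.**

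| Test | 0% disc. | 2% | 5% | 10% |
|---|---|---|---|---|
| Wald, converged | 70.5 | 75.6 | 74.5 | 66.5 |
| Wald, Fisher if a cell is empty | 87.6 | 83.2 | 76.7 | 66.8 |
| Boschloo | 88.6 | 83.6 | 76.3 | 65.1 |
| Fisher throughout | 85.5 | 79.8 | 71.5 | 59.1 |
| Likelihood ratio | 91.5 | 86.7 | 79.5 | 68.9 |
| Corrected two-proportion z | 82.3 | 76.2 | 68.2 | 57.6 |

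The 87.6 is 70.5 + 17.1. At 5% the gain is 76.7 − 74.5 = 2.2 points. Plain Wald power rises when a few subjects drop out, because 40/40 becomes rarer.

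**Exact size at nominal 0.05.** Wald with Fisher for empty cells: maximum 0.057 near a null rate of 0.50, 0.048 at 0.70, 0.018 at 0.90. Plain Wald has the same maximum. Boschloo: at most 0.048. Likelihood ratio: up to 0.091 near 0.95.

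**The case against.** The strongest reply is that the loss is conditional twice over. No section says Wald, and an analyst facing a 40/40 arm would notice a diverging estimate and would not simply accept a p-value near 1. SAP 11.0 also requires deviations from the plan to be described and justified in the study report. This stands as a limit on the claim. A reader might infer that the trial will lose 17 points of power or that a perfect active arm cannot win; the documents do not support that, because they leave the test open. But justification after the fact does not replace choosing the test beforehand, and the open choice is itself the defect.

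The second reply is that 17.2% is high. SAP 5.0 ties its rates to an evaluable sample, while the FAS includes everyone randomized and counts discontinuations as failures. This stands too. At an assumed 3% discontinuation plain Wald already exceeds the planned corrected z (75.9% vs 73.4%), and at 5% the empty-cell rule is worth only about 2 points.

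A reader might also conclude that 80.8% is wrong. It is not an arithmetic error; it belongs to a different test from the one in SAP 9.1. Nor can it be said that a 20/20 active arm at the interim would read as futile, since SAP 7.4 does not define its Z as this model's Wald statistic.

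**Conclusion.** The point holds as an omission that should be fixed. The primary test is not identified, and the plan's own assumptions make the case in which the tests disagree most up to 17.2% likely. Between the two most usual readings of the model, Wald and likelihood ratio, exact power differs by 91.5 − 70.5 = 21 points at the design rates and by 79.5 − 74.5 = 5 points at an assumed 5% discontinuation. Under the Wald reading, power at the design rates falls below the stated 80%, and a stronger result can fail where a weaker one succeeds.

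These figures assume 40 per arm, no random effect, a normal reference for Wald, a fit run to convergence and no stopping at the futility look. A fit cut off early could give a different p-value for the same table. The size of the problem depends on a discontinuation rate that the documents do not give, and shrinks quickly as that rate rises.

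**What to change.** Before unblinding, name in SAP 9.1 one primary test that is valid with a zero cell, state its reference distribution, and state that the model has no random effect. The reference matters: with t on 78 degrees of freedom (an assumption), Wald power at 10% discontinuation is 64.8%, not 66.5%, and size at a null rate of 0.70 is 0.043, not 0.048. Either of two choices would do:

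- An exact test such as Boschloo's, which keeps size at or below 0.05 at every null rate.
- The model's Wald test, with Fisher's exact p-value when either arm has no failures or no successes. The SAP should then note that size reaches 0.057 near a null rate of 0.50.

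Fisher throughout is also valid, but conservative. The likelihood-ratio test should not become the default without noting its size of up to 0.091.

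State that the same rule applies in SAP 9.2.1. Restate the power for the chosen test in SAP 5.0 and 7.4 and, at the next amendment, in Protocol 9.2 and the synopsis, which carry the same 80% statement.

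The cost is SAP wording, a less familiar or two-step test, and a changed power figure. No further subjects or data are needed. The test itself needs no protocol amendment, because SAP 1.0 gives the SAP precedence. Boschloo gives up 66.5 − 65.1 = 1.4 points to plain Wald (normal reference) at an assumed 10% discontinuation; the Wald-with-Fisher rule was not below plain Wald at any rate checked.

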1. PROTOCOL SYNOPSIS

A Phase 2, Randomized, Double-Blind, Placebo-controlled Study of the Safety and Efficacy of STI-5656 (Abivertinib Maleate) in Subjects Hospitalized Due to COVID-19

Protocol Number: STI-5656-2001, Version 4.0

Investigator(s)/ Study Centers

This study will be conducted at multiple study centers located in the United States.

Phase: 2

Objectives

Primary Objective:

- To assess the efficacy of STI-5656 in subjects with severe coronavirus disease 2019 (COVID-19)

Secondary Objectives:

- To assess the safety and tolerability of STI-5656 in subjects with severe COVID-19
- To assess the pharmacokinetic profile in the study population

Endpoints

Primary Endpoint:

- Proportion of subject alive and free of respiratory failure at Day 28

Respiratory failure, is defined based on resource utilization of any of the following modalities:

- Noninvasive positive pressure ventilation or continuous positive airway pressure
- Endotracheal intubation and mechanical ventilation
- Oxygen delivered by high-flow nasal cannula (heated, humidified, oxygen delivered via reinforced nasal cannula at flow rates >20 L/min with fraction of delivered oxygen ≥ 0.5)
- Extracorporeal membrane oxygenation (ECMO)

Secondary Endpoints:

- Types, frequencies, and severities of adverse events (AEs) and the relationships of AEs to IP; includes serious adverse events (SAEs)
- Proportion of subjects alive and free of respiratory failure at Day 60
- Change in clinical status (on a 0-8-point ordinal scale)¹ of subject at Day 7, Day 14 and Day 28

¹ 8-category ordinal scale of patient health status ranges: 0=no clinical or virological evidence of infection; 1=no limitation of activities; 2=limitation of activities; 3=hospitalized, no oxygen therapy; 4=oxygen by mask or nasal prongs; 5=non-invasive ventilation or high-flow oxygen; 6=intubation and mechanical ventilation; 7=ventilation + additional organ support – pressors, rapid response team (RRT), extracorporeal membrane oxygenation (ECMO); 8=death. See [Section 14.2](#) for form.

- Proportion of subjects alive and discharged from Intensive Care Units (ICU) at Days 14 and 28
- Time from randomization to first occurrence of respiratory failure or death on study due to any cause up to Day 28
- Percent change from baseline in CRP at Days 3, 5, 7, 10, 14, 28
- Relative change from baseline in oxygenation index (PaO₂/FiO₂) up to Day 5
- All-cause mortality at Day 60 and Day 90

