5.1. Subject Inclusion Criteria

Subjects are eligible to be included in the study only if all the following criteria apply:

1. Confirmed infection with SARS-CoV-2 per World Health Organization (WHO) criteria (including positive RT-PCR nucleic acid test of any specimen [eg, respiratory, blood, urine, stool, or other bodily fluid]) within 7 days of randomization. Positive RT-PCR test results more than 7 days prior to randomization is allowed if the site is unable to obtain a repeat sample and if the subject has progressive disease consistent with COVID-19.
2. COVID-19 pneumonia (documented radiographically) requiring hospitalization and oxygen saturation <94% on room air or subject requires supplemental oxygen.
3. Age ≥ 18 years at the time of signing the informed consent form
4. Subject or family member/caregiver must have provided written informed consent which includes signing the institutional review board approved consent form prior to participating in any study related activity. However, if obtaining written informed consent is not possible, other procedures as provided in the March 27th, 2020 FDA Guidance on Conduct of Clinical Trials of Medical Products during COVID-19 Pandemic, Question 10, may be used.
5. Able to swallow capsules
6. Willing to follow contraception guidelines

If a female, be sterile (surgically or biologically)* or at least one year post-menopausal**, or have a monogamous partner who is surgically sterile, or have a same sex partner, or if in a heterosexual relationship, must agree to do the following for at least 1 month after receiving IP:

- Practice abstinence
- Use at least 1 of the following medically acceptable methods of birth control:
 - Hormonal methods such as oral, implantable, injectable, vaginal ring, or transdermal contraceptives (must have started a minimum of 1 full cycle, based on the subject's usual menstrual cycle period, before IP dose)
 - Intrauterine device
 - Double-barrier method (condoms, sponge, or diaphragm with spermicidal jellies or cream).

**Defined as having had a hysterectomy and/or bilateral oophorectomy, bilateral salpingectomy or bilateral tubal ligation/occlusion at least 6 weeks prior to screening; or having a congenital or acquired condition that prevents childbearing*

***Defined as at least 12 months with no menses without an alternative medical cause)

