### 9.2.2 Clinical Status

The 8-point ordinal scale will be summarized descriptively by treatment group and study day. The last known clinical status will be used for days with missing clinical status. All post-baseline days with missing ordinal scale score will use the previous last known clinical status.

Additionally, stacked bar charts will be presented for the proportion of subjects in each category by group and study day.

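### The primary endpoint has no prespecified analysis adjusted for baseline respiratory support; one stratified analysis on a score already collected would guard this 80-subject trial against chance imbalance

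*SAP*

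**What the plan says.** SAP 9.1 and Protocol 9.4.3 give the same primary model, binomial with a logit link: "The model will include group as a fixed effect". No other term is named. The one further analysis of this endpoint is optional: "Sensitivity analyses may be performed using PP population".

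Protocol 6.7 and SAP 4.0 describe 1:1 allocation through the IRT and name no stratification factor. Inclusion criterion 2 (Protocol 5.1) reads "COVID-19 pneumonia (documented radiographically) requiring hospitalization and oxygen saturation <94% on room air or subject requires supplemental oxygen"; neither it nor the exclusions in 5.2 state an explicit upper limit on oxygen support. That is shown for the supplied protocol only ("Protocol Number: STI-5656-2001, Version 4.0"). The SAP is written to "V5.0 dated 07Dec2020", which was not available.

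The ordinal score is collected at Screening and on Day 1 (Protocol Table 1, 8.2.1, 8.2.2). SAP 8.2 states "Demographic/baseline characteristics will be summarized descriptively by treatment group in Safety Population", but its variable list contains neither the score nor oxygen support. Protocol 9.4.5 modelled clinical status with the Day 1 value as covariate. SAP 9.2.2, which takes precedence under SAP 1.0, plans only description: "The 8-point ordinal scale will be summarized descriptively by treatment group and study day". Baseline adjustment remains in the MMRM analyses of SAP 9.2.3 and 9.3, which concern other endpoints.

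**The concern.** Score 5 or higher covers non-invasive ventilation, high-flow oxygen, intubation and ECMO, largely the same modalities that count as failure at Day 28. Baseline support is therefore a natural candidate for a strong prognostic factor. With 40 per arm and no stratified allocation, the arms can differ on it by chance. The unadjusted difference then carries that imbalance, and the plan has no prespecified analysis to separate it from a drug effect. An adjustment chosen after unblinding would carry less weight. The risk runs both ways: a gap favouring active raises the chance of a false claim, and a gap against active costs power.

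**Working it through.** **The plan's own figure.** Inputs from SAP 5.0 and 7.4: success 95.7% against 70% (difference 0.257), two-sided alpha 0.05, 40 per arm. With mean proportion 0.8285:

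n = [1.96·√(2·0.8285·0.1715) + 0.8416·√(0.957·0.043 + 0.70·0.30)]² / 0.257² = 32.6

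With continuity correction: n/4 · [1 + √(1 + 4/(n·0.257))]² = 39.97, so 40. Power at 40 is 80.0%, against 80% stated in SAP 5.0 and 80.8% in 7.4. The sample size reproduces.

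**Assumptions, not in the documents.** Share *s* at score 5 or higher: 15-50%. Odds ratio for failure, score 5 or higher against the rest: 3-10. Control failure is held at 30% overall: *s*·p₁ + (1−*s*)·p₀ = 0.30. This gives p₁ = 41-74% and p₀ = 9-26%.

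**How often the arms differ.** The count at score 5 or higher in each arm is binomial(40, *s*). The probability of a gap of at least 4, in either direction, is 27.0% at *s* = 15%, 39.3% at 30% and 43.4% at 50%. Half of these favour active: 13.5% to 21.7%.

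**How far a gap moves the estimate.** Worked case, *s* = 40% and odds ratio 5: p₀ = 1/6 and p₁ = 1/2 (check: 0.4·0.5 + 0.6·0.167 = 0.30).

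- No drug effect: a 10-point gap moves the unadjusted difference by 10·(0.500 − 0.167) = 3.3 points. Over the whole range: 2.2-5.2 points.
- Planned effect (4.3% failure on active, common odds ratio within strata, so 1.7% and 8.1% by stratum), gap split evenly between arms: 5·(0.500 − 0.167) + 5·(0.081 − 0.017) = 2.0 points, about 8% of 25.7. Over the range: about 1.3-3.3 points, or 5-13% of 25.7.

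**What it does to the test.** Simulation at 40 per arm with 400,000 or more trials per scenario and no continuity correction; repeat runs agree to about 0.3 point. The Pearson test is the score test of the group-only logit model, and CMH is its stratified counterpart.

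| Quantity | Group-only (Pearson) | Stratified (CMH) |
|---|---|---|
| Two-sided type I error, all trials | 4.8-4.9% | 4.9-5.1% |
| False benefit given a gap of at least 4 favouring active (nominal 2.5%) | about 4.6-8.0% | 2.4-2.8% |
| Power at the planned effect, all trials | 91.5% | about 91-94% |

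CMH power by odds ratio is 91.0-91.4% at 3, 91.9-92.4% at 5 and 93.3-94.1% at 10. These uncorrected figures are not comparable with the corrected 80.8% in SAP 7.4.

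Mirror case: with 25% at score 5 or higher, odds ratio 5 and a 13 against 7 split to the disadvantage of active, likelihood ratio power is 83.6% group-only and 92.7% adjusted.

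SAP 9.1 does not name the test of the logit model. With a Wald test, power is 70.5% group-only and 68.0-74.9% with the factor added. The level is low because an active arm with no failures, which has probability 0.957⁴⁰ = 17%, counts as non-significant.

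**The case against.** An unadjusted comparison in a randomised trial is legitimate, and nothing above shows an error in it. The excess of false claims after a favourable gap is balanced by a deficit after an unfavourable one (0.2-1.0% over the same range), so overall error is as planned. A reader might infer that the primary test is invalid or the trial underpowered; the calculations contradict both.

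The sizes also rest on assumed inputs. Inclusion criterion 5 requires the ability to swallow capsules, which works against entry of intubated subjects, and the time-to-first-respiratory-failure endpoint suits entrants not yet in failure. That criterion does not exclude high-flow oxygen or non-invasive ventilation, but the share could be small. At a 10% share and odds ratio 1.5, a favourable gap of at least 4 occurs in roughly 9% of trials and false benefit in them is 2.9%. With a factor of no prognostic value, CMH costs about 1 point of power. This stands.

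Four stronger readings go beyond the documents:

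- *That the SAP has no baseline adjustment at all.* The MMRM analyses in 9.2.3 and 9.3 have it; the gap concerns the primary endpoint.
- *That an imbalance would go unseen.* It could show indirectly in the by-day ordinal summary (9.2.2), PaO₂/FiO₂ (9.2.3), the respiratory status listing (10.3) and oxygen saturation (10.4).
- *That a 10-point gap is worth 9-20% of the planned effect.* That divides the no-effect shift by 25.7; at the planned effect it is 5-13%.
- *That the 0.537 futility bound is unaffected by stratification.* Crossing rates simulated at the planned effect with 20 per arm (3.5% unstratified, 2.4-3.4% stratified) omit the continuity correction behind the SAP's cumulative beta of 0.065, so they do not settle it.

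**Conclusion.** The point holds as an improvement in robustness. The primary endpoint lacks a prespecified analysis adjusted for baseline support, although the score is already collected. On the assumed share (15-50%) and odds ratio (3-10), about 14-22% of trials would have a gap of at least 4 of 40 favouring active. In these the false-benefit rate would be roughly two to three times nominal without stratification and close to nominal with it. Average power is not the argument: it changes by about −1 to +3 points with CMH. If few subjects enter at score 5 or higher, or the score predicts weakly, the benefit is small. The reading of the eligibility criteria applies to protocol Version 4.0 only. Confidence is medium, because the documents fix neither the share nor its risk.

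**What to change.** Before unblinding, add to SAP 9.1 one analysis of the primary endpoint in the full analysis set, stratified by the last ordinal score before first dose (before randomisation if never dosed), 5 or higher against 4 or lower. Use a CMH test with a Mantel-Haenszel risk difference. Either:

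- make it primary and keep the group-only logit model as a sensitivity analysis; or
- at minimum, name it as a supportive analysis beside the group-only primary. This closes most of the gap without replacing the primary test.

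Call the factor level of support. Score 5 takes in any high-flow oxygen, while the endpoint sets flow and oxygen-fraction limits, so the factor is not baseline respiratory failure. Take it from the ordinal score: the support categories listed in Protocol 8.1.8 do not separate high-flow oxygen or non-invasive ventilation. Add it to the SAP 8.2 table.

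If the stratified analysis becomes primary, also:

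- state that the reported effect measure is the risk difference;
- say in SAP 9.2.1 whether the stratum carries over, since that section provides that "The same method used in the primary endpoint will be repeated for the following secondary efficacy endpoints";
- say in SAP 7.4 whether the interim Z is stratified, and recompute the 0.537 bound on the SAP's continuity-corrected basis.

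Cost: a few sentences and no new data; a possible change of effect measure; and a possible power loss of about 1 point with CMH, or up to about 2.5 points (70.5% to 68.0%) if the adjusted logit model is tested by Wald.
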